11.6. Statistical Analysis

No formal statistical testing of safety data is planned.

11.7. Interim Analyses

There are no planned interim analyses. However, the accumulating data during study conduct may be used for reporting required for health authority submissions or other purposes. As this is a non-comparative study without formal hypotheses, any interim data may be used for purely administrative purposes without having an impact on study conduct or need for statistical

adjustments. All interim reporting must be approved by the study responsible physician and project statistician prior to conduct.

12. ADVERSE EVENT REPORTING

Timely, accurate, and complete reporting and analysis of safety information from clinical studies are crucial for the protection of subjects, investigators, and the sponsor, and are mandated by regulatory agencies worldwide. The sponsor has established Standard Operating Procedures in conformity with regulatory requirements worldwide to ensure appropriate reporting of safety information; all clinical studies conducted by the sponsor or its affiliates will be conducted in accordance with those procedures.

12.1. Definitions

12.1.1. Adverse Event Definitions and Classifications

Serious Adverse Event

A serious adverse event based on ICH and EU Guidelines on Pharmacovigilance for Medicinal Products for Human Use is any untoward medical occurrence that at any dose:

- Results in death
- Is life-threatening (The subject was at risk of death at the time of the event. It does not refer to an event that hypothetically might have caused death if it were more severe.)
- Requires inpatient hospitalization or prolongation of existing hospitalization
- Results in persistent or significant disability/incapacity
- Is a congenital anomaly/birth defect
- Is a suspected transmission of any infectious agent via a medicinal product
- Is Medically Important*

*Medical and scientific judgment should be exercised in deciding whether expedited reporting is also appropriate in other situations, such as important medical events that may not be immediately life threatening or result in death or hospitalization but may jeopardize the subject or may require intervention to prevent one of the other outcomes listed in the definition above. These should usually be considered serious.

If a serious and unexpected adverse event occurs for which there is evidence suggesting a causal relationship between the study vaccine and the event, the event must be reported as a serious and unexpected suspected adverse reaction (SUSAR) even if it is a component of the study endpoint (eg., all-cause mortality).

Unlisted (Unexpected) Adverse Event/Reference Safety Information

An adverse event is considered unlisted if the nature or severity is not consistent with the applicable product reference safety information. For Ad6.ZEBOV and MVA-BN-Filo, the

expectedness of an adverse event will be determined by whether or not it is listed in the Investigator's Brochure and Addenda, if applicable. ^{5,6}

Adverse Event With a Causal Relationship to a Study Vaccine

An adverse event is considered to have a causal relationship to a study vaccine if the attribution is possible, probable, or very likely by the definitions listed in Section 12.1.2.

An adverse event is considered to have no causal relationship to the study vaccine if the attribution is not related or doubtful by the definitions listed in Section 12.1.2.

12.1.2. Attribution Definitions

Every effort should be made by the investigator to explain any adverse event and to assess its potential causal relationship, ie, to administration of the study vaccine or to alternative causes, eg, natural history of underlying disease(s), concomitant drug(s). This applies to all adverse events, whether serious or non-serious. Assessment of causality must be done by a licensed study physician (the investigator or designee).

The investigator will use the following guidelines to assess the causal relationship of an adverse event to study vaccine:

Not Related

An adverse event that is not related to the use of the study vaccine.

Doubtful

An adverse event for which an alternative explanation is more likely, eg, concomitant drug(s), concomitant disease(s), or the relationship in time suggests that a causal relationship is unlikely.

Possible

An adverse event that might be due to the use of the study vaccine. An alternative explanation, eg, concomitant drug(s), concomitant disease(s), is inconclusive. The relationship in time is reasonable; therefore, the causal relationship cannot be excluded.

Probable

An adverse event that might be due to the use of the study vaccine. The relationship in time is suggestive. An alternative explanation is less likely, eg, concomitant drug(s), concomitant disease(s).

Very Likely

An adverse event that is listed as a possible adverse reaction and cannot be reasonably explained by an alternative explanation, eg, concomitant drug(s), concomitant disease(s). The relationship in time is very suggestive.

12.1.3. Severity Criteria

An assessment of severity grade will be made using the following general categorical descriptors:

Mild: Awareness of symptoms that are easily tolerated, causing minimal discomfort and not interfering with everyday activities.

Moderate: Sufficient discomfort is present to cause interference with normal activity.

Severe: Extreme distress, causing significant impairment of functioning or incapacitation. Prevents normal everyday activities.

The investigator should use clinical judgment in assessing the severity of events not directly experienced by the subject (eg, laboratory abnormalities).

12.2. Special Reporting Situations

Safety events of interest on a sponsor study vaccine that may require expedited reporting and/or safety evaluation include, but are not limited to:

Adverse events of special interest known for Ad26.ZEBOV and MVA-BN-Filo^{5,6}

These safety events may not meet the definition of an adverse event; however, from a policy perspective, they are treated in the same manner as adverse events. Any special situation that meets the criteria of a serious adverse event should be recorded on a Serious Adverse Event Report Form and be reported to the local sponsor within 24 hours of them becoming aware of the event.

12.3. Procedures

12.3.1. Serious Adverse Events

All serious adverse events occurring during the study must be reported to the appropriate sponsor contact person by study-site personnel within 24 hours of their knowledge of the event.

Information regarding serious adverse events will be transmitted to the sponsor using the Serious Adverse Event Form, which must be completed and signed by a physician from the study site, and transmitted to the sponsor within 24 hours. The initial and follow-up reports of a serious adverse event should be made by facsimile (fax).

All serious adverse events that have not resolved by the end of the study, or that have not resolved upon discontinuation of the subject's participation in the study, must be followed until any of the following occurs:

- The event resolves
- The event stabilizes
- The event returns to baseline, if a baseline value/status is available

- The event can be attributed to agents other than the study drug or to factors unrelated to study conduct
- It becomes unlikely that any additional information can be obtained (subject or health care practitioner refusal to provide additional information, lost to follow-up after demonstration of due diligence with follow-up efforts)

Suspected transmission of an infectious agent by a medicinal product will be reported as a serious adverse event. Any event requiring hospitalization (or prolongation of hospitalization) that occurs during the course of a subject's participation in a study must be reported as a serious adverse event, except hospitalizations for the following:

- Hospitalizations not intended to treat an acute illness or adverse event (eg, social reasons such as pending placement in long-term care facility)
- Surgery or procedure planned before entry into the study (must be documented in the CRF).
 Note: Hospitalizations that were planned before the signing of the ICF for the current study, and where the underlying condition for which the hospitalization was planned has not worsened, will not be considered serious adverse events. Any adverse event that results in a prolongation of the originally planned hospitalization is to be reported as a new serious adverse event.

The cause of death of a subject in a study, whether or not the event is expected or associated with the study vaccine, is considered a serious adverse event.

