1. COHORT 1: VACCINATED SUBJECTS

Data collection schedule for subjects exposed to Ad26.ZEBOV and/or MVA-BN-Filo (or placebo) in a Phase 1, 2 or 3 clinical study:

	Visit 1 ^a	Contact 2 ^a	Subsequent Contacts ^a	End of Study ^a
	Baseline (Start of Data Collection) ^b	Month 6	Every 6 Months	After 60 Months of Follow-up ^c
Subject information				
Subject consent ^d	X			
Selection criteria	X			
Demographics ^e	X			
Ongoing subject review				
Serious adverse events ^{e,f}	X	X	X	X
Medication and vaccinations ^{e,g}	X	X	X	X
Study completion/withdrawal				
End-of-study form				$X^{\mathbf{h}}$

- a. Only the first visit is a study site visit (and may coincide with the last visit in the subject's original study); data collection at other time points will preferably occur through phone calls. If not possible by phone, a study site visit needs to be organized.
- b. Data collection can start when a signed informed consent form (ICF) is available for the current study. Preferably, this occurs at the last visit of the subject's original study. If this is not possible, baseline data will be collected when a signed ICF is available and data will be captured retrospectively from the subject's last visit in the original study up to the moment of enrollment in the current study.
- c. The subject should be followed for a total of 60 months after prime vaccination, including the duration in the subject's original study.
- d. Before the start of data collection in this study, all subjects and/or their legally-acceptable representative (where applicable) must sign an ICF for the current study indicating that he or she understands the purpose of and procedures required for the study and is willing to participate in the study.
- e. Relevant data will be copied from the analysis data set of the subject's original study. Any relevant new information should be added in the Case Report Form (CRF) of the current study.
- f. All serious adverse events are to be documented for a total of 60 months after prime vaccination (including the duration in the subject's original study).
- g. Any medication taken within a period of 30 days prior to the onset of a serious adverse event and up to the resolution of the serious adverse event.
- h. When an enrolled subject completes or withdraws from the study, or is lost to follow-up, the investigator will complete the end-of-study form for the individual subject and provide a specific date for the end-of-study observation(s).

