1.2.4. Potential Risks

The following potential risks for Ad26.ZEBOV and MVA-BN-Filo will be considered in this study, taking into consideration that this rollover study does not include further administration of the candidate vaccines during the study period:

Vaccine Induced Seropositivity (VISP)

In general, uninfected subjects who participate in Ebola vaccine studies may develop Ebola-specific antibodies as a result of an immune response to the candidate Ebola vaccine, referred to as VISP. These antibodies may be detected in Ebola serologic tests, causing the test to appear positive even in the absence of actual Ebola infection. VISP may become evident during the study, or after the study has been completed.

Pregnancy and Birth Control

The effect of the study vaccines on a fetus or nursing baby is unknown, as well as the effect on semen. Therefore, a pregnancy with estimated conception within 28 days of vaccination with MVA-BN-Filo or within 3 months of vaccination with Ad26.ZEBOV in a female subject vaccinated with Ad26.ZEBOV and/or MVA-BN-Filo in Phase 1, 2 or 3 clinical studies will be followed up in this study. This study includes no further requirements for birth control as all rollover subjects have completed the vaccination phase.

There may be other serious risks that are not known.

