The study will consist of an enrollment visit, a number of follow-up contacts and an end-of-study contact. These contacts are preferably conducted by phone; if not possible, a study site visit needs to be organized. Preferably, offspring from vaccinated female subjects will visit the study site for every study visit. If not possible, the child may be visited at home by study site staff or a qualified health care worker for data collection.

Data collection can start when a signed informed consent form (ICF) is available for the current study. Preferably, signing of the ICF occurs at the last visit of the subject's original study (or at birth for offspring). If this is not possible, baseline data will be collected when a signed ICF is available and data need to be captured retrospectively up to the moment of enrollment in the current study.

Data collection will be as follows for the 3 cohorts:

Cohort 1: Data for subjects vaccinated with Ad26.ZEBOV and/or MVA-BN-Filo (or placebo) in a Phase 1, 2 or 3 clinical study (adults, adolescents and children) and who consent to participation in the current study will be collected in 6-month intervals. Data collection will continue for a total of 60 months after prime vaccination (including the duration in the subject's original study).

Cohort 2: Data on the pregnancy outcome of female subjects who became pregnant with estimated conception within 28 days after vaccination with MVA-BN-Filo (or placebo) or within 3 months after vaccination with Ad26.ZEBOV (or placebo) in a Phase 1, 2 or 3 clinical study

and who consent to participation in the current study will be collected at notification of the pregnancy, and at the end of the pregnancy. These subjects will be followed in Cohort 2 up to the end of their pregnancy. Thereafter, female subjects will continue to be followed in Cohort 1 (to reach a total of 60 months follow-up after prime vaccination including the duration in the subject's original study); live-born children will be followed in Cohort 3.

Cohort 3: Data for children born to female subjects exposed to Ad26.ZEBOV and/or MVA-BN-Filo (or placebo) in a Phase 1, 2 or 3 clinical study who became pregnant with estimated conception within 28 days after vaccination with MVA-BN-Filo (or placebo) or within 3 months after vaccination with Ad26.ZEBOV (or placebo) and for whom consent for the current study is given will be collected in 6-month intervals and up to 60 months after birth.

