11.1. Endpoints

The following endpoints will be analyzed:

- Incidence of serious adverse events in subjects exposed to Ad26.ZEBOV and/or MVA-BN-Filo in a Phase 1, 2 or 3 clinical study, up to 60 months after prime vaccination.
- Incidence of pregnancy with estimated conception within 28 days after vaccination with MVA-BN-Filo or within 3 months after vaccination with Ad26.ZEBOV.
- Incidence of pregnancy by pregnancy outcome.
- Incidence of live-born children from a pregnancy with estimated conception within 28 days after vaccination with MVA-BN-Filo or within 3 months after vaccination with Ad26.ZEBOV.
- Incidence of serious adverse events in children born from a pregnancy with estimated conception within 28 days after vaccination with MVA-BN-Filo or within 3 months after vaccination with Ad26.ZEBOV up to 60 months after birth.

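### The planned-hospitalization exclusion is dated from the roll-over consent, but the Cohort 1 SAE endpoint starts at prime vaccination, so a narrow set of post-vaccination admissions may not be classified as SAEs

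*Protocol*

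**What the plan says.** **The exclusion.** Section 12.3.1 states the general rule that an event requiring hospitalization during a subject's "participation in a study must be reported as a serious adverse event, except hospitalizations for the following". The second exception listed is "Surgery or procedure planned before entry into the study (must be documented in the CRF"). A Note under that exception names the date that counts. It covers "Hospitalizations that were planned before the signing of the ICF for the current study" and says these are not SAEs if the underlying condition has not worsened. An adverse event that prolongs the planned stay is still reported as a new SAE.

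**The SAE window.** The first endpoint in Section 11.1 is SAE incidence in exposed subjects "in a Phase 1, 2 or 3 clinical study, up to 60 months after prime vaccination". Footnote f of the Cohort 1 Time and Events Schedule agrees: "All serious adverse events are to be documented for a total of 60 months after prime vaccination", and it counts the time spent in the original study. For Cohort 3, footnote e of its schedule starts SAE collection at birth.

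**When consent is signed.** Section 5.1 requires Cohort 1 subjects to have been exposed already, and Section 1.2.4 says that "all rollover subjects have completed the vaccination phase". Section 3.1 adds: "Preferably, signing of the ICF occurs at the last visit" of the original study (or at birth for offspring). If that is not possible, consent comes later and the gap is captured retrospectively.

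**Earlier events.** For demographics, SAEs and medication, footnote e of the Cohort 1 schedule says: "Relevant data will be copied from the analysis data set" of the original study.

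**The concern.** An exclusion for pre-planned admissions normally keeps out hospital stays already arranged before the subject was exposed. It does so when consent precedes exposure. In this roll-over study the order is reversed: exposure comes first and the consent that dates the exclusion comes later. Between the two lies a stretch of the SAE window in which a new condition can arise and an admission for it can be scheduled. Section 12.3.1 asks when the admission was planned and whether the condition has worsened. It does not ask whether the condition predates vaccination.

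This affects more than a reporting form. Section 11.5 analyzes what has been classified as an SAE, so an admission excluded at the site enters neither the percentage of subjects with an event nor the rate per person-year. It also falls outside 24-hour SAE reporting, and Section 8 collects medication only around SAEs. In a descriptive study with no hypothesis, absolute SAE incidence is itself the result.

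**Working it through.** No arithmetic applies. The protocol gives no figure for this rule, no time from prime vaccination to the roll-over consent, and no share of SAEs that are serious only because of a planned admission. The check is therefore one of date order and wording.

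**Step 1: date order in Cohort 1.** From Sections 1.2.4, 3.1 and 5.1 and footnotes b and f of the Cohort 1 schedule:

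prime vaccination (window opens) < last original-study visit ≤ roll-over consent (exclusion date) < month 60 (window closes).

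The exclusion date thus always falls after the window has opened.

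**Step 2: apply Section 12.3.1 to each pattern of dates.** The cases assume no worsening, no prolongation and no other ground of seriousness.

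| Condition arises | Admission planned | Admission takes place | Treatment as written |
|---|---|---|---|
| Before vaccination | Before vaccination | After roll-over consent | Excluded; a window-start date would give the same answer |
| After vaccination | Before roll-over consent | After roll-over consent | Excluded, although the condition arose inside the window |
| After vaccination | After roll-over consent | After roll-over consent | SAE |
| After vaccination | During the original study | During the original study | Governed by the original study's rules; an SAE recorded there is copied over |
| After vaccination | Between last original-study visit and a late consent | Same gap | Unclear |

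The second row is the point.

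**Step 3: conditions needed for a net omission in row 2.** All five must hold:

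1. The admission was planned before the roll-over consent.
2. The condition has not worsened (Section 12.3.1).
3. The stay is not prolonged (Section 12.3.1).
4. No other criterion in Section 12.1.1, including medical importance, makes the event serious.
5. The original study did not already record the event as an SAE. If it did, the record is copied over and counts in the 60-month incidence.

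Condition 5 matters. With consent at the last original-study visit, both the onset and the planning fall inside the original study. Whether that study recorded an SAE depends on protocols not shown here.

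**Step 4: the other cohorts.** In Cohort 3 the window opens at birth. Where consent is signed at birth there is no gap. Where it is signed later, the row 2 pattern can occur, but only for non-congenital conditions, since Section 12.1.1 makes a congenital anomaly serious in its own right. Cohort 2's own SAE collection starts at enrollment (Cohort 2 schedule, footnote e) and is not affected. Women who move on to Cohort 1 come under the Cohort 1 window.

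**Step 5: direction.** An unclassified admission can only lower the count of events or of affected subjects, so any effect on absolute incidence is downward.

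**The case against.** The strongest reply is that no net loss has been shown. SAEs already recorded in the original study are copied over whatever Section 12.3.1 says, and the original protocols that would settle how often this happens are not available. This stands. It is why condition 5 is part of the point and why the under-count is called possible.

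Second, the exclusion may be narrower than the Note suggests when read alone, because the Note sits under the exception for planned surgery or procedures. Deaths, life-threatening or disabling events and medically important conditions stay serious in any case. This also stands. What remains is mainly stable conditions with a scheduled procedure.

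Third, planned surgery or procedures must be entered in the CRF, and Section 11.5 allows additional listings, so cases can be found. That helps with identification, but it does not put them into the SAE percentages or rates.

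A reader might also infer three stronger things that the protocol does not support:

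- *That reported SAE incidence is biased downward as a matter of fact.* Too much depends on the original studies to say so.
- *That planned admissions between the last original-study visit and a late consent are lost.* The governing sentence concerns hospitalization during participation, while the Note speaks of anything planned before consent. The wording is ambiguous, which is a reason to clarify it and not evidence of loss.
- *That the rule favours the vaccine over placebo.* It applies alike to both, and Sections 2.2 and 11.6 plan no hypothesis and no formal test.

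**Conclusion.** The mismatch holds: Section 12.3.1 dates the exclusion from the roll-over consent, while Section 11.1 and the Cohort 1 schedule open the SAE window at prime vaccination, and no other section reconciles them. High confidence applies to that textual mismatch only.

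The consequence is a possible under-count of absolute SAE incidence in Cohort 1 and, with consent after birth, in Cohort 3. Its size cannot be calculated from the protocol and is probably small, because all five conditions must be met together. That judgement assumes that few admissions are serious solely because they were planned hospital stays, which the protocol neither confirms nor contradicts. The point is worth considering because the correction is specific and brings the event definition into line with the study's own endpoint. It does not threaten the study's conclusions.

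**What to change.** Reconcile Section 12.3.1 with Section 11.1 and the Cohort 1 and Cohort 3 schedules:

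- Limit the exclusion to hospitalizations planned before the start of the cohort's SAE window: prime vaccination for Cohort 1, including women who move there from Cohort 2, and birth for Cohort 3.
- Use one definition for both SAE reporting and endpoint counting, so that the two do not diverge.
- State that the definition also covers events captured retrospectively between the last original-study visit (or birth) and a late consent.
- For subjects already enrolled, use the planned procedures documented in the CRF to identify affected cases and reclassify them where needed.

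The text change is a sentence or two, plus a line in the CRF completion guidelines. Because Section 12.3.1 is protocol text, it needs a formal amendment with ethics committee approval under Section 17.1. There will be some additional SAE reports, including a few for stable pre-existing conditions whose admission was scheduled only after vaccination. SAEs copied from the original studies keep those studies' definitions, so the 60-month endpoint may not be fully uniform even after the change.
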